## **STUDY SUMMARY/SYNOPSIS**

TITLE	Effects of e-cigarettes vs usual care for smoking cessation when offered at homeless centres: A cluster randomised controlled trial				
SHORT TITLE	Smoking CEssation Trial in Centres for the Homeless/SCeTCH				
Protocol Version	1.1				
Number and Date	20.01.22				
Methodology	Cluster randomised controlled trial (cRCT)				
Study Duration	36 months				
Study Centre(s)	32 homeless centres across Great Britain				
Objectives	
 
Primary: To determine the 6-month sustained, biochemically validated abstinence rates in smokers using EC compared to smokers offered UC.
 
Secondary:
 
1. Among those who have not achieved full abstinence, to compare the number reporting at least fifty percent smoking reduction at 24 weeks in the EC versus the UC arm.
 
2. To compare the number achieving 7-day point prevalence quit rates at 4-, 12- and 24-week follow-up in the EC versus the UC arm.
 
3. To document changes in risky smoking practices (e.g., sharing cigarettes, smoking discarded cigarettes) from baseline to 4-, 12- and 24-weeks in both EC and UC arm.
 
4. To determine the cost-effectiveness of the intervention
 
5. To document fidelity of intervention implementation; mechanisms of change; contextual influences and sustainability.
 
				
Number of Subjects/Patients	480 randomised participants				
Main Inclusion/Exclusion Criteria	Inclusion criteria: Participants aged 18+, self-reported daily smoking as verified by staff working at the homeless centres, known to centre staff and willing and able to provide written informed consent.  Exclusion criteria: Pregnant or breastfeeding, a never or former smoker, currently using a smoking cessation aid, unable or unwilling to provide consent, not known to the centre staff, allergic to any of the e-liquid ingredients (EC arm only).				

## Statistical Methodology and Analysis

Sustained CO validated smoking cessation at 24-weeks using the Russell Standard for cessation trials and intention to treat analysis (i.e. no more than 5 cigarettes since 2 weeks post target quit date [TQD] validated by expired CO <8ppm.Participants lost to follow-up are treated as non-abstainers. Abstinence rates and rates of those sustaining a 50% or greater reduction in baseline cigarette consumption and CO levels will be compared between the study arms. Reductions in the frequency risky smoking practices will be compared between study arms. Frequency of adverse reactions will be compared between arms.

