#### 4.5 Measures

- Demographic details, smoking history and housing status
- Fagerstrom Test of Cigarette Dependence (FTCD) (17)
- Motivation to Stop Smoking Scale (MTSS; (18))
- Adverse reactions 13 adverse reactions (nervous, headache, sweaty, weak, nausea, pounding heart, throat/mouth irritation, sleep disturbance, dizziness, shortness of breath, cough, wheezy, phlegm production) based on those reported in our feasibility study (5), the Cochrane review of EC (3) and the English TEC study (19), each rated on a 5-point scale from 1 (not at all) to 5 (extremely)
- Positive effects 5 positive effects (hit, pleasant, satisfying, tastes good, helpful for reducing urge to smoke) based on those most commonly reported in our feasibility study (5)
- Risky smoking practices (sharing cigarettes, pickup up discarded cigarettes, asking strangers for cigarettes) each rated on a 4-point scale (not at all, occasionally, regularly, daily)
- Thoughts about EC (perceptions of harm, usefulness for quitting, acceptability)
- EC support (i.e. from staff at centres and others)
- Unintended consequences (of supplying free EC starter kits) including theft, loss, exchanges, breakages, adding other substances.
- Self-reported smoking status
- End-expired carbon monoxide reading: Collected using a calibrated CO monitor. A reading of <8ppm will be used as a cut-off for abstinence

- Use of EC/NRT (including use in the UC arm). Participants who stop using EC/NRT will also be asked their reasons for doing so.
- European Quality of Life-5 Dimensions (EQ5D) questionnaire at baseline and each follow up point.
- Smoking cessation service and health service use at baseline and each follow up point.
- Use of personal and social services
- AUDIT-C
- Diagnoses of mental illness: binary yes/no response

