## 5 Adverse event/reaction reporting

## **5.1 General Definitions**

## 5.1.1 Adverse Event (AE) and Adverse Reaction (AR)

An AE is any untoward medical occurrence in a participant who has undergone any research procedure including occurrences which are not necessarily caused by or related to that product. An AE can therefore be any unfavourable and unintended sign (including an abnormal laboratory finding), symptom or disease temporarily associated with the use of the study product.

An AR is an AE that may have a causal relationship with the research procedure that the participant has undergone. All AEs judged by either the reporting investigator or the Sponsor as having a reasonable causal relationship to the study treatment qualify as an AR.

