#### 5.2.2 Relatedness

The PI or delegate will assess whether there is a reasonable possibility that the AE is related to a trial treatment or procedure.

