## 5.2.3 Expectedness

The following ARs are deemed potentially related to the study treatment: nausea, throat/mouth irritation, cough, headache, sweaty, weak and sleep disturbance and these will be rated at each follow up point. The PI or delegate will use this list to determine whether the AE is an expected reaction to the trial treatment or procedure.

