## 6.2 Secondary Endpoints

- CO validated sustained abstinence rates at 4, 12 and 24 weeks post
- 7-day point prevalence abstinence at 4, 12 and 24 weeks
- 50% Smoking reduction in participants who did not achieve full abstinence at 24 weeks
- Changes in the frequencies of risky smoking practices from baseline to 4, 12 and 24 weeks
- Adverse reactions
- Cost-effectiveness of the interventions over the 24 week trial period.

Abstinence at 4 weeks after TQD would be defined as a self-report of no smoking of conventional cigarettes (not a puff) for the previous 2 weeks, validated by a CO reading of <8ppm. Participants who do not provide a CO reading at Week 4 will be considered to be smoking. 12 and 24 week sustained abstinence will be calculated in accordance with the Russell Standard [50] as a self-report of smoking no more than 5 cigarettes since 2 weeks post-TQD validated by CO readings < 8ppm. Participants lost to follow-up or not providing biochemical validation will be included as non-abstainers.

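### The between-arm safety endpoint is called adverse reactions, but the protocol gives that term two conflicting meanings and does not say which is compared; the causality-judged one would not give a fair comparison

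*Protocol*

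**What the plan says.** The protocol synopsis (Statistical Methodology and Analysis) says "Frequency of adverse reactions will be compared between arms". Section 6.2 lists "Adverse reactions" among the secondary endpoints, with no time point, summary measure or cross-reference.

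The term is then used in two ways.

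- **Causality-judged event.** Section 5.1.1: "An AR is an AE that may have a causal relationship with the research procedure that the participant has undergone". It adds that events judged by the investigator or sponsor as "having a reasonable causal relationship to the study treatment qualify as an AR". Under section 5.2.2 the PI or a delegate will "assess whether there is a reasonable possibility that the AE is related to a trial treatment or procedure". Section 5.3 makes this a recorded CRF/REDCap field and equates a related AE with an AR.
- **Symptom checklist.** Section 4.5 lists 13 adverse reactions, "each rated on a 5-point scale from 1 (not at all) to 5 (extremely"). No causal link is required. Table 1 has a row for adverse effects at baseline, 4, 12 and 24 weeks. That row lacks the EC-arm label that some other rows carry.

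Section 5.2.3 adds a shorter list of reactions deemed potentially related to treatment: "nausea, throat/mouth irritation, cough, headache, sweaty, weak and sleep disturbance and these will be rated at each follow up point". It is used to judge whether an event was expected.

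**The concern.** A between-arm comparison needs an outcome that is ascertained in the same way in both arms. A symptom checklist completed by everyone meets that condition. An event that counts only after someone has judged it related to treatment may not. In this trial one arm receives an inhaled nicotine product (section 4.7) and the other a leaflet and signposting (section 4.4, Control Group). The same cough is more readily attributed to vapour than to a leaflet, and the protocol describes no masking of the relatedness judgement.

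Both variables will be in the database, and both carry the endpoint's name. An analyst who follows the formal definition in section 5 would compare attributed events. One who follows section 4.5 would compare ratings. The two could give different answers on the safety of EC, and nothing in the protocol fixes the choice before the data are seen.

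**Working it through.** **Step 1: can the text settle the meaning?**

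| Place | What an adverse reaction is | Causality needed? | Who decides |
|---|---|---|---|
| 5.1.1, 5.2.2, 5.3 | AE judged related to treatment or procedure | Yes | PI or delegate; sponsor |
| 4.5, Table 1 | 13 symptoms rated 1 to 5 | No | Participant |
| 5.2.3, 5.2.4 | 7 of those symptoms, used for expectedness | Deemed potentially related in advance | Fixed list, participant-rated |
| Synopsis, 6.2 | Not stated | Not stated | Not stated |

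The objectives (2.1) and the secondary outcomes (4.6.2) do not mention adverse reactions, so they do not resolve it.

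**Step 2: how large could the attribution effect be?** The protocol gives no rate, power or sample size for this endpoint, so there is no figure to reproduce. This step is an illustration.

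Inputs from section 6.3: 240 participants per arm, cluster size 15, ICC 0.01. That ICC was set for the primary outcome; using it here is an assumption.

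- Design effect = 1 + (15 − 1) × 0.01 = 1.14.
- Effective n per arm = 240 / 1.14 = 210.5.
- AR rate in an arm = true symptom rate × share attributed to treatment.
- Chance of a significant EC excess (two-sided 0.05) = Φ[(pE − pU − 1.96 × SE0) / SE1], where SE0 = √[2p̄(1 − p̄)/210.5] and SE1 = √{[pE(1 − pE) + pU(1 − pU)]/210.5}.

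As a check, the same formula gives 90.7% for 6.25% vs 0.5% (section 6.3 states 90%). For 5% vs 0.5% it gives 80.8% at ICC 0.01 (stated 81%) and 73.9% at ICC 0.025 (stated 74%).

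Assumed for the illustration: the true symptom rate is the same in both arms, and only attribution differs.

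| True rate, both arms | Attributed, EC vs UC | AR rate, EC vs UC | Chance of significant EC excess |
|---|---|---|---|
| 10% | 50% vs 5% | 5.0% vs 0.5% | 81% |
| 20% | 50% vs 5% | 10% vs 1% | 98% |
| 40% | 50% vs 5% | 20% vs 2% | over 99% |
| 10% | 50% vs 25% | 5.0% vs 2.5% | 27% |
| 20% | 50% vs 25% | 10% vs 5% | 50% |
| 40% | 50% vs 25% | 20% vs 10% | 82% |

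First row worked through: p̄ = 0.0275, SE0 = 0.0159, SE1 = 0.0158, so (0.045 − 1.96 × 0.0159)/0.0158 ≈ 0.87 and Φ(0.87) ≈ 0.81. The normal approximation is rough there, since only 240 × 0.005 = 1.2 UC events are expected.

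With equal attribution, or with the checklist and no attribution step, the two arms have the same expected rate and the error rate stays at the nominal 5%.

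**Step 3: the shorter list.** Section 5.2.3 names 7 of the 13 items. The other 13 − 7 = 6 are nervous, pounding heart, dizziness, shortness of breath, wheezy and phlegm production. The sentence says the seven are rated at each follow-up. It does not say that only the seven are.

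**The case against.** The strongest reply is that the checklist is the natural reading. Section 4.5 is the list of trial measures and uses the endpoint's own label, Table 1 schedules the ratings in both arms, and section 5 is about safety reporting. On that reading no attribution bias arises. Much of this stands, and the checklist may well be what is intended. But section 5.1.1 is the only formal definition, and section 5.3 turns it into a recorded data field, so the other reading is a literal one too.

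Three stronger readings are tempting, and the documents do not support them.

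- *That the comparison is loaded against EC by definition, because a reaction must be caused by a product only EC participants receive.* Only the AE definition mentions the product ("symptom or disease temporarily associated with the use of the study product"). The AR wording in sections 5.1.1 and 5.2.2 refers to a research procedure, or a trial treatment or procedure, and Table 1 lists usual care as an intervention. A UC participant can formally have an AR. The bias is likely if the causality-judged meaning is used; it is not built into the definition.
- *That the baseline ratings are ignored.* They are collected. The synopsis and section 6.2 say nothing about how they enter the analysis, and silence is not exclusion. The analysis plan may cover it. Pre-existing symptoms would also be counted under the same rule in both arms.
- *That six symptoms will have no follow-up data.* Section 5.2.3 is an expectedness list, and sections 4.5 and 4.9 point to all 13 being rated.

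It is also fair to say that section 5.3 records AEs separately from relatedness, so a tabulation irrespective of causality is already possible.

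**Conclusion.** The point holds as a conflict of definition. The protocol names one between-arm safety endpoint and gives its name two incompatible meanings, only one of which supports a fair comparison. Which variable is the endpoint is for the protocol to fix, and here its own sections disagree.

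The consequence is conditional. If causality-judged reactions are compared, a significant false EC excess could arise in about 27% to over 99% of trials. That range rests on assumed attribution of 50% in EC against 5% to 25% in UC, equal true symptom rates of 10% to 40%, a single symptom, and the primary outcome's ICC. The documents support none of these rates, so the range shows the mechanism and is not a forecast. If the checklist is compared, this bias does not arise, although participants who know what they received still rate their own symptoms.

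**What to change.** - **Synopsis and section 6.2:** state that the safety endpoint is the 13 participant-rated symptoms of section 4.5 at 4, 12 and 24 weeks, in both arms, irrespective of attribution, compared between arms with adjustment for the baseline rating.
- **Same places:** add that AEs and SAEs are tabulated by arm irrespective of causality.
- **Section 5:** keep the causality-judged AR for descriptive safety reporting, and say that it is not the variable used for the between-arm comparison. Calling the section 4.5 list participant-rated symptoms would remove the clash of names.
- **Section 5.2.3:** say that the seven-item list serves only to judge expectedness and does not limit which of the 13 items are rated at follow-up.

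The cost is wording. Table 1 already schedules the ratings at baseline and every follow-up, and section 5.3 already records AEs and SAEs separately from relatedness.

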## **GLOSSARY**

GLUSSAK					
AE	Adverse Event				
AL	Area Leads				
AR	Adverse Reaction				
CCA	Complete Case Analysis				
CEAC	Cost-Effectiveness Acceptability Curves				
CI	Co-Investigator				
CO	Carbon Monoxide				
CPD	Cigarettes Per Day				
cRCT	Cluster Randomised Controlled Trial				
CRF	Case Record Forms				
CRN	Clinical Research Network				
DMC	Data Monitoring Committee				
EC	Electronic Cigarette				
EOI	Expression of Interest				
EQ5D	European Quality of Life -5 Dimensions				
FTCD	Fagerstrom Test of Cigarette Dependence				
GCP	Good Clinical Practice				
HSR	Health, Safety and Resilience				
ICC	Intraclass Correlation Coefficient				
ICER	Incremental Cost-Effectiveness Ratio				
ITT	Intention To Treat				
KCL	King's College London				
LSBU	London South Bank University				
MCID	•				
MHRA	Minimally Clinical Important Difference				
MTSS	Medicines and Healthcare products Regulatory Agency				
NCSCT	Motivation to Stop Smoking Scale  National Centre for Smoking Cessation and Training				
NHS	National Health Service				
NICE	National Institute for Health and Care Excellence				
NIHR	National Institute for Health Research				
NRT	Nicotine Replacement Therapy				
PHE	Public Health England				
PI	Principal Investigator				
PPI	Patient and Public Involvement				
PSS	Personal and Social Services				
QA	Quality Assurance				
QALYs	Quality Adjusted Life Years				
QC	Quality Control				
RA	Research Assistant				
RCT	Randomised Controlled Trial				
REC	Research Ethics Committee				
RR	Risk Ratio				
SAE	Serious Adverse Event				
SAR	Serious Adverse Reaction				
SSS	Stop Smoking Service				
SUSAR	Suspected Unexpected Serious Adverse Reaction				
TEC	Trial of Electronic Cigarettes				
TM	Trial Manager				
TMF	Trial Master File				
TMG	Trial Management Group				
TQD	Target Quit Date				
TSC	Trial Steering Committee				
	·				

UC	Usual Care
VBA	Very Brief Advice

## 1 Introduction

## 1.1 Background

Electronic cigarettes (EC) are electronic vaping devices that are handheld and produce for inhalation, an aerosol formed by heating an e-liquid using a battery-powered heating coil (1).

EC are the most popular quit method used by smokers in the UK (2), and there is growing evidence for their effectiveness in clinical trials (3). EC may be a useful method of quitting for people who are heavily nicotine dependent as they are effective in delivering nicotine over and above other nicotine products. To date, there is less evidence on how effective EC are for smoking cessation for people with pre-existing severe health and social needs. This evidence is needed to fully evaluate their public health and population impact (4).

This study explores the effectiveness of EC versus usual care (UC) in people accessing homeless support services. At the current time, in these settings, UC involves a referral to a traditional NHS stop smoking service (SSS). SSS provide licensed Nicotine Replacement Therapies (NRT) alongside behavioural support. While these methods are effective for many, for others, including those with competing needs, this may not be enough. EC with effective nicotine delivery and ability to replicate some of the sensory aspects of smoking (e.g., hand to mouth action, deep inhalation) may enhance quit rates. Offering EC at a place which people who are experiencing homelessness are already seeking support, may also be advantageous (5).

## 1.2 Feasibility Data

To explore the feasibility of offering EC to adult smokers accessing homeless services, we conducted a cluster feasibility trial in four centres; three were in England and one was in Scotland (5,6). In this trial, two clusters were assigned to offer participants usual care (UC) which consisted of the standard offer of referral to the local SSS and two clusters offered participants a free EC starter pack, which consisted of one refillable battery-operated EC device and e-liquid provided once per week for 4-weeks. The results showed the intervention was acceptable to both staff and participants. We were able to meet our progression criteria as over half of all participants invited were recruited to the study (N=80 in a 5-month period) and we exceeded 50% retention at each follow up point. We were also able to collect the majority of the information needed for an economic evaluation and reports of unintended consequences (e.g., adverse effects, trading the device) were very low. The 24-week sustained biochemically validated abstinence [ITT] rates were 6.25% [EC] vs. 0% [UC]).

## Effects of EC on smoking

Evidence for the efficacy of EC for smoking cessation is accumulating; in the most recent living Cochrane review published in 2021 (3), across 3 RCTs with 1498 smokers, there was moderate certainty that EC were almost twice as effective as NRT for long-term (defined as 12-months) smoking cessation (RR: 1.69; CI 1.25 - 2.27). Higher quit rates were also found with EC compared with behavioural support across 4 studies (N = 2312; RR: 2.5; CI 1.24-5.04) although the certainty here was low due to imprecision and risk of bias. EC may therefore be a viable alternative to traditional pharmacotherapies for smoking cessation for adults experiencing homelessness, especially if offered free of charge at homeless centres where relationships with staff are already established.

### EC safety

The most recent Public Health England (PHE) evidence review of the literature (7) presents MHRA yellow card notifications of injuries associated with EC use. To date, these are minimal but there are 3 known fatalities, which may be associated with, but not causally related to, EC use.

In the most recent Cochrane review (3), there was imprecision in the findings on safety as measured by reports of AE and SAEs (the confidence intervals were wide). However, comparison analysis revealed no difference in AEs between nicotine and non-nicotine EC use. Incidents associated with SAE and EC use were low. While there is no clear evidence on the harms associated with nicotine EC use, the report concludes that there remains only a small number of studies by which to analyse and within those, follow-up times are less than desirable to measure health and safety outcomes.

In our feasibility study, 21 possible AE were rated, each on a scale of 0 (not at all) to 100 (extreme). The most commonly reported effects were nervousness, headache, sweating, weakness and nausea, each with a mean score below 20. Nausea and headache along with cough and throat/mouth irritation were also the most commonly reported AE in the Cochrane EC review.

Other areas of safety concern have focused on e-liquid content and vapour emissions. While not risk free, it is now well-evidenced that EC are far less hazardous to the user and bystanders than cigarette smoke, with substantially less toxicants and carcinogens detected in exclusive users (4,7,8). A recently published analysis of 40,785 e-liquid containing products ingredient and emission data to the MHRA from November 2016 to October 2017 (9), highlighted some areas for improvement and concern, notably the large range of ingredients and emissions. The MHRA reporting system is unstandardized in terms of reporting requirements, and for quantified emissions, median levels are for the most part below published safe limits for ambient air. However, the authors conclude that, notwithstanding these suggested improvements, EC remain safer than combustible tobacco smoking. As flavours appeal to smokers switching to EC, a balanced approach to reducing absolute risk while not making the products unappealing is required.

## 1.3 Rationale and Risks/Benefits

People experiencing homelessness have some of the worse health outcomes of all minority and disadvantaged groups, whereas the health inequalities between those in the most advantaged social grades can be described as a slope, the relative disparity between those housed and not housed is more akin to a cliff (10). Smoking is incredibly common amongst this population, up to four times the average UK smoking prevalence rate (11,12). Smoking significantly contributes to excessive morbidity and mortality (10,13,14). At the same time, there is a paucity of evidence of tobacco dependence treatment for this group (11,15). There is strong evidence to suggest tailored interventions, designed to provide support at a place which is already familiar to the person, with established relationships and taking a harm reduction approach, may help people to quit smoking (5,6,11,15,16).

More broadly, as the evidence on EC continues to grow, whether EC can support people facing severe health and social comorbidities is lacking. That is, while EC may assist people to remain smoke free without such competing needs, their effectiveness for more disadvantaged groups requires greater attention. Indeed, turning attention to groups facing disadvantage, was a recommendation in the recent Cochrane review (3). If EC are effective for such groups, they can reduce the burden of smoking related disease within poorer communities and would signal a population wide net positive public health benefit.

Our feasibility study tested whether the offer of an EC was acceptable and whether a full trial would be possible. Early results were promising, and this trial now builds on this work. The aim of this trial is to conduct a two-arm multi-centre cluster randomised controlled trial (cRCT). The following research questions will be answered.

- 1. What is the effectiveness and cost-effectiveness of providing free EC starter kits to smokers accessing homeless centres compared with UC?
- 2. How is the EC intervention implemented and how does organisational and geographic context influence implementation?
- 3. What are the mechanisms through which the delivered intervention activities and participant interactions produce change in smoking behaviour?
- 4. If the intervention is effective and cost-effective, what are the facilitators and barriers to successful implementation across Great Britain?

